For each of the unsolicited AE, SAE, and pIMD endpoints the number of participants and percentage will be summarized regardless of MedDRA classification and by system organ class and by preferred term within system organ class for each study group.

Separate summaries will be produced for the following categories:

- AE of any grade
- AEs of any grade that are possibly or probably related to vaccine(s)
- Grade 3 AE
- Grade 3 AE that are possibly or probably related to vaccine(s)
- MAE of any grade
- pIMDs
- SAEs
- SAEs related to vaccine
- Fatal SAE
- Fatal SAE related to vaccine

Data listings of all AEs will be provided by participant. In addition, AEs in the categories above will be provided as listed data.

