10.5.3.1 Assessment of Intensity and Causality

Assessment of Intensity

The intensity of the following solicited AEs will be assessed as described:

Table 13 Intensity Scales for Solicited Events in Adults 18 Years of Age or Older

Adults (≥18 years)		
Event	Intensity grade	Parameter
Pain at administration site	0	None
	1	Mild: Any pain neither interfering with nor preventing normal everyday activities.
	2	Moderate: Painful when limb is moved and interferes with everyday activities.
	3	Severe: Significant pain at rest. Prevents normal everyday activities.
Headache	0	Normal
	1	Mild: Headache that is easily tolerated.
	2	Moderate: Headache that interferes with normal activity.
	3	Severe: Headache that prevents normal activity.
Fatigue	0	Normal
	1	Mild: Fatigue that is easily tolerated.
	2	Moderate: Fatigue that interferes with normal activity.
	3	Severe: Fatigue that prevents normal activity.
Muscle ache all over body	0	Normal
	1	Mild: Muscle aches that are easily tolerated.
	2	Moderate: Muscle aches that interfere with normal activity.
	3	Severe: Muscle aches that prevent normal activity.
Joint pain	0	Normal
	1	Mild: Joint pain that is easily tolerated.
	2	Moderate: Joint pain that interferes with normal activity.

	3	Severe: Joint pain that prevents normal activity.	
Shivering (chills)	0	Normal	
	1	Mild: Shivering (chills) that is easily tolerated.	
	2	Moderate: Shivering (chills) that interferes with normal activity.	
	3	Severe: Shivering (chills) that prevents normal activity.	
Sweating	0	Normal	
	1	Mild: Sweating that is easily tolerated.	
	2	Moderate: Sweating that interferes with normal activity.	
	3	Severe: Sweating that prevents normal activity.	
Gastrointestinal symptoms: nausea, vomiting, diarrhea and/or abdominal pain	0	Normal	
	1	Mild: Gastrointestinal symptoms that are easily tolerated.	
	2	Moderate: Gastrointestinal symptoms that interfere with normal activity.	
	3	Severe: Gastrointestinal symptoms that prevent normal activity.	
Redness at administration site		Record greatest surface diameter in mm	
Swelling at administration site		Record greatest surface diameter in mm	
Temperature		Record temperature in °C/°F. Oral route is preferred.	

The maximum intensity of local injection site redness/swelling will be scored as follows:

- 0: ≤ 20 mm
- 1: > 20 to 50 mm
- 2: > 50 to 100 mm
- 3: > 100 mm

The maximum intensity of fever will be scored as follows:

- 0: $< 38.0^{\circ}\text{C}$ ($< 100.4^{\circ}\text{F}$)

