- 1: $\geq 38.0 - 38.4^{\circ}\text{C}$ ($\geq 100.4 - 101.2^{\circ}\text{F}$)
- 2: $\geq 38.5 - 38.9^{\circ}\text{C}$ ($\geq 101.3 - 102.1^{\circ}\text{F}$)
- 3: $\geq 39.0 - 40.0^{\circ}\text{C}$ ($\geq 102.2 - 104.0^{\circ}\text{F}$)
- 4: $> 40.0^{\circ}\text{C}$ ($> 104.0^{\circ}\text{F}$)

The investigator will assess the maximum intensity that occurred over the duration of the event for all unsolicited AEs (including SAEs) recorded during the study. The assessment will be based on

the investigator's clinical judgement.

The following definitions are to be used to rate the severity of an AE:

- Mild: A type of AE that is usually transient and may require only minimal treatment or therapeutic intervention. The event does not generally interfere with usual activities of daily living.
- Moderate: A type of AE that is usually alleviated with additional specific therapeutic intervention. The event interferes with usual activities of daily living, causing discomfort but poses no significant or permanent risk of harm to the research participant.
- Severe: A type of AE that interrupts usual activities of daily living, or significantly affects clinical status, or may require intensive therapeutic intervention.

An AE that is assessed as Grade 3 (severe) should not be confused with an SAE. Grade 3 is a category used for rating the intensity of an event; and both AEs and SAEs can be assessed as Grade 3. An event is defined as 'serious' when it meets 1 of the predefined outcomes as described in the Section [10.5.2](#).

Assessment of Causality

- The investigator is obligated to assess the relationship between study intervention and each occurrence of each AE/SAE/pIMD. The investigator will use clinical judgment to determine the relationship.
- A *reasonable possibility* of a relationship conveys that there are facts, evidence, and/or arguments to suggest a causal relationship, rather than a relationship cannot be ruled out.
- Alternative causes, such as underlying disease(s), concomitant therapy, and other risk factors, as well as the temporal relationship of the event to study intervention administration, will be considered and investigated.
- For causality assessments, events assessed as having a reasonable possibility of being related to study intervention will be considered "related." Events assessed as having no reasonable possibility of being related to study intervention will be considered "unrelated."

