	1	Mild: Shivering (chills) that is easily tolerated.
	2	Moderate: Shivering (chills) that interferes with normal activity.
	3	Severe: Shivering (chills) that prevents normal activity.
Sweating	0	Normal
	1	Mild: Sweating that is easily tolerated.
	2	Moderate: Sweating that interferes with normal activity.
	3	Severe: Sweating that prevents normal activity.
Gastrointestinal symptoms: nausea, vomiting, diarrhea and/or abdominal pain	0	Normal
	1	Mild: Gastrointestinal symptoms that are easily tolerated.
	2	Moderate: Gastrointestinal symptoms that interfere with normal activity.
	3	Severe: Gastrointestinal symptoms that prevent normal activity.
Redness at administration site		Record greatest surface diameter in mm

Document: \\ieedc-vnasc01\BIOSdata\GSK\H5N8(Flu)\HAB99808\Biostatistics\Documentation\SAP\SAP\SAP v5.0\GSK H5N8-219833\_SAP\_v5.0\_19AUG2024.docx

Author: PPD

Version Number: 5.0

Version Date: 19AUG2024

Template No.: CS\_TP\_BS016 Revision 7

Reference: CS\_WI\_BS005

Effective Date: 01Nov2021

Adults (<math>\geq 18</math> years)		
Event	Intensity grade	Parameter
Swelling at administration site		Record greatest surface diameter in mm
Temperature		Record temperature in $^{\circ}\text{C}/^{\circ}\text{F}$ . Oral route is preferred.

Table G: Intensity scales for solicited events – erythema / swelling and fever

	Erythema/swelling	Fever (Temp <math>^{\circ}\text{C}</math>)
0:	$\leq 20$ mm	$<38.0$ $^{\circ}\text{C}$ $(<100.4$ $^{\circ}\text{F})$
1:	$> 20 - \leq 50$ mm	$\geq 38.0$ $^{\circ}\text{C}$ ( $100.4$ $^{\circ}\text{F}$ ) - $\leq 38.4$ $^{\circ}\text{C}$ ( $101.2$ $^{\circ}\text{F}$ )
2:	$> 50 - \leq 100$ mm	$\geq 38.5$ $^{\circ}\text{C}$ ( $101.3$ $^{\circ}\text{F}$ ) - $\leq 38.9$ $^{\circ}\text{C}$ ( $102.1$ $^{\circ}\text{F}$ )
3:	$> 100$ mm	$\geq 39.0$ $^{\circ}\text{C}$ ( $102.2$ $^{\circ}\text{F}$ ) - $\leq 40.0$ $^{\circ}\text{C}$ ( $104.0$ $^{\circ}\text{F}$ )
4:		$>40.0$ $^{\circ}\text{C}$ ( $104.0$ $^{\circ}\text{F}$ )

Solicited events will be summarized and listed as:

- The number and percentage of participants, with exact 95% CIs, reporting each individual solicited administration site AE (pain, erythema/swelling, swelling) for all grades, grade  $\geq 2$ , grade  $\geq 3$ , medically attended events during the 7-day follow-up period, and ongoing at the end of the 7-day follow-up period will be tabulated following each vaccination and overall.

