- The number and percentage of participants, with exact 95% CIs, reporting each individual solicited systemic AE (fatigue, fever, headache, muscle ache, joint pain, shivering [chills], sweating, gastrointestinal symptoms [nausea, vomiting, diarrhea, abdominal pain]) for all grades, grade  $\geq 2$ , grade  $\geq 3$ , medically attended events during the 7-day follow-up period, and ongoing at the end of the 7-day follow-up period will be tabulated following each vaccination and overall.
- The number and percentage of participants, with exact 95% CIs, reporting any solicited administration site AE, any solicited systemic AE and any solicited AE (across all administration site and systemic symptoms), for all grades, grade  $\geq 2$ , grade  $\geq 3$ , medically attended events during the 7-day follow-up period will be tabulated following each vaccination and overall.

Document: \\ieedc-vnasc01\BIOSdata\GSK\H5N8(Flu)\HAB99808\Biostatistics\Documentation\SAP\SAP\SAP v5.0\GSK H5N8-219833\_SAP\_v5.0\_19AUG2024.docx

Author: PPD

Version Number: 5.0

Version Date: 19AUG2024

Template No.: CS\_TP\_BS016 Revision 7

Reference: CS\_WI\_BS005

Effective Date: 01Nov2021

- Duration of solicited events reported during the 7-day follow-up period will be tabulated for each individual solicited event using descriptive statistics (mean, minimum, Q1, median, Q3, maximum).. The start date is the first during the 7-day solicitation period with the symptom at grade > 0 while the stop date is the last day with the symptom at grade > 0 in or beyond the solicited period. In addition, the duration for specific grade(s) (grade  $\geq$  2, grade  $\geq$  3 and medically attended solicited events) for each symptom defined as the number of days in the reporting period with grade above or equal to specific grade will be summarized.
- All solicited administration site events will be included in a listing. Prolonged solicited AEs that continue beyond the 7-day follow-up period will be identified using a flag in the listing of solicited administration site events.
- All solicited systemic events will be included in a listing. Prolonged solicited AEs that continue beyond the 7-day follow-up period will be identified using a flag in the listing of solicited systemic events.

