### **16.1.2. Unsolicited Adverse Events**

All unsolicited adverse events summaries will be reported by MedDRA, SOC and PT and will include non-serious unsolicited events, SAE and AESI. These summaries will exclude solicited AE starting within day 1 to 7 and continuing beyond day 7.

The verbatim reports of unsolicited AEs will be reviewed by a physician and the signs and symptoms will be coded according to the MedDRA Dictionary for Adverse Reaction Terminology version 25.1 or higher. Every verbatim term will be matched with the appropriate Preferred Term.

Unsolicited events will be summarized and listed as:

The number and percentage of participants, with exact 95% CIs, with any unsolicited AEs during the 21-day follow-up period (i.e., the day of vaccination and 20 subsequent days) will be tabulated following each vaccination and overall.

This summary will be repeated for:

- grade  $\geq$  3 unsolicited AEs,
- causally related unsolicited AEs
- causally related and grade  $\geq$  3 unsolicited AEs,

---

Document: \\ieedc-vnasc01\BIOSdata\GSK\H5N8(Flu)\HAB99808\Biostatistics\Documentation\SAP\SAP\SAP v5.0\GSK H5N8-219833\_SAP\_v5.0\_19AUG2024.docx

Author: PPD Version Number: 5.0

Version Date: 19AUG2024

Template No.: CS\_TP\_BS016 Revision 7

Reference: CS\_WI\_BS005

Effective Date: 01Nov2021

- unsolicited AEs resulting in a medically attended visit

A list of unsolicited AEs leading to study discontinuation or vaccine discontinuation will be tabulated by study intervention group by MedDRA, SOC and PT.

All unsolicited AEs will be included in a listing.

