### **16.1.3.     Solicited and Unsolicited Adverse Events**

For clinicaltrials.gov and EudraCT posting purposes, the following summary will be produced:

The number and percentage of participants reporting any unsolicited adverse events with MedDRA PTs that are synonymous with solicited events, and starting after the end of each solicited period, will be summarized following each vaccination and overall and by severity (mild, moderate or severe). If a participant experiences an event on more than one occasion, the maximum intensity will be reported. **Error! Reference source not found.** shows the corresponding MedDRA LLTs that will be selected from the unsolicited adverse events for this analysis.

Table H:     Solicited events lower level term codes and decodes

Solicited event	Lower level term code	Corresponding Lower level term decode
Pain	10022086	Injection site pain
Erythema	10022061	Injection site erythema
Swelling	10053425	Injection site swelling
Fever	10016558	Fever
Headache	10019211	Headache
Fatigue	10016256	Fatigue
Myalgia	10028411	Myalgia
Arthralgia	10003239	Arthralgia
Chills	10008531	Chills
Nausea	10028813	Nausea
Vomiting	10047700	Vomiting
Diarrhoea	10012735	Diarrhoea
Abdominal pain	10000081	Abdominal pain

The number and percentage of participants, with exact 95% CIs, of combined solicited and unsolicited non-serious adverse events (all grades, Grade 3, medically attended) during the 21-day follow-up period (i.e., the day of

Document: \\ieedc-vnasc01\BIOSdata\GSK\H5N8(Flu)\HAB99808\Biostatistics\Documentation\SAP\SAP\SAP\SAP v5.0\GSK H5N8-219833\_SAP\_v5.0\_19AUG2024.docx

Author: PPD

Version Number: 5.0

Version Date: 19AUG2024

Template No.: CS\_TP\_BS016 Revision 7

Reference: CS\_WI\_BS005

Effective Date: 01Nov2021

vaccination and 20 subsequent days) will be produced by SOC and PT, according to occurrence of each event, following each vaccination and overall. The number of events will also be provided in which 2 events are considered different if they have different start date or PT name.

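### SAP 16.1.3 cuts the combined adverse event table at Grade 3 rather than grade ≥ 3, so, read literally, a non-serious Grade 4 fever would miss the severe row

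*SAP*

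**What the plan says.** SAP 16.1.3 plans a table of "combined solicited and unsolicited non-serious adverse events" over the 21 days after each vaccination, by system organ class and preferred term, with exact 95% confidence intervals. Its breakdown is "all grades, Grade 3, medically attended".

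The two preceding sections cut severity differently. SAP 16.1.1 tabulates each individual solicited event at grade ≥ 2 and grade ≥ 3. It does the same for participants "reporting any solicited administration site AE, any solicited systemic AE and any solicited AE (across all administration site and systemic symptoms". SAP 16.1.2 repeats its unsolicited summary for "grade $\geq$ 3 unsolicited AEs", and again for those that are also causally related. Protocol 9.4.3.2 uses grade ≥ 2 and grade ≥ 3 for solicited events.

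Fever is graded 0 to 4 in both documents: in protocol 10.5.3.1, under "The maximum intensity of fever will be scored as follows", and in SAP Table G, "Intensity scales for solicited events – erythema / swelling and fever". Grade 3 runs from 39.0 to 40.0 °C, and Grade 4 is anything above 40.0 °C. No other solicited event has a Grade 4.

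**The concern.** A programmer who follows SAP 16.1.3 as written would filter on grade equal to 3. A fever above 40.0 °C would pass the all-grades filter and fail the severe one, so the omission would fall on the most extreme values of the one event that has a Grade 4. The fever row of this table could then disagree with the fever row of the solicited table for the same participant. Neither document says that Grade 3 here means Grade 3 or higher. At stake are the internal consistency of the safety outputs and the count of severe fever in one table. The conclusions of the trial are not at stake.

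**Working it through.** The documents state no figure on this point, so there is nothing to reproduce. The check compares the wording, applies the two filters to the fever scale, and then illustrates the size.

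**1. Severity cuts side by side**

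| Place | Events covered | Severe cut |
|---|---|---|
| SAP 16.1.1 | solicited, 7 days | grade ≥ 3 |
| SAP 16.1.2 | unsolicited, 21 days | grade ≥ 3 |
| SAP 16.1.3 | solicited and unsolicited combined, non-serious, 21 days | Grade 3 |
| Protocol 9.4.3.2 | solicited, 7 days | grade ≥ 3 |
| Protocol 9.4.3.2 | unsolicited AEs, SAEs, pIMDs | Grade 3 |

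**2. Is a Grade 4 event within the scope of the combined table?** Yes. Fever is a solicited systemic event in SAP Table E, and the table includes solicited events unless they are serious.

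**3. The two filters applied to SAP Table G**

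| Temperature (°C) | Grade | Passes grade = 3 | Passes grade ≥ 3 |
|---|---|---|---|
| 38.9 | 2 | no | no |
| 39.0 | 3 | yes | yes |
| 40.0 | 3 | yes | yes |
| 40.1 | 4 | no | yes |

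The filters differ only above 40.0 °C, and so only for fever.

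**4. Repeated readings.** Protocol 9.4.3.2 counts a recurring solicited event once per participant, at its maximal severity. If that rule is carried into the combined table (an assumption, because SAP 16.1.3 does not say so), a participant with 39.5 °C on one day and 40.2 °C on the next is classed as Grade 4. That participant leaves the Grade 3 fever row altogether.

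**5. Which rows lose a case?** The fever preferred-term row does. A line counting participants with any Grade 3 event loses the participant only if he or she has no other Grade 3 event.

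**6. Illustrative size.** Inputs: n = 65 planned per age subgroup and dose group (SAP 2.5), and an assumed number x of participants whose only high-grade event is a Grade 4 fever. The percentage is 100·x/n. The exact (Clopper-Pearson) 95% limits are the beta quantiles B(0.025; x, n − x + 1) and B(0.975; x + 1, n − x), with a lower limit of 0 when x = 0.

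| Assumed Grade 4 fevers | Literal Grade 3 line | Grade ≥ 3 line |
|---|---|---|
| 1 | 0/65 = 0.0% (0.0 to 5.5) | 1/65 = 1.5% (0.04 to 8.3) |
| 2 | 0/65 = 0.0% (0.0 to 5.5) | 2/65 = 3.1% (0.4 to 10.7) |

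With no Grade 4 fever, the two lines are identical.

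**The case against.** The best defence is that Grade 3 is shorthand for severe. Unsolicited events are rated mild, moderate or severe, with severe as the top level. Every solicited scale except fever also stops at 3, and SAP 16.1.3 itself speaks of mild, moderate or severe in its first summary. The SAP leaves detailed table content to templates and mock shells, which are not among the documents, and these may already have the cumulative cut. This is plausible, and it is why the effect is conditional on a literal reading. It does not settle the matter, because the two sections just before write ≥ 3 explicitly and no text equates the two forms.

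It can also be said that nothing is lost. A Grade 4 fever still appears in the individual and pooled grade ≥ 3 tables of SAP 16.1.1, in its duration summary, in the listings, and in the all-grades line of the combined table. This is correct and confines the matter to one output.

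A reader might draw three stronger conclusions, none of which the documents support.

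- **That protocol 9.4.3.2 has the same gap**, since it lists categories such as "Grade 3 AE that are possibly or probably related to vaccine(s". That list covers unsolicited AEs, SAEs and pIMDs. Protocol 10.5.3.1 has the investigator rate unsolicited AEs, including SAEs, as mild, moderate or severe, with Grade 3 as severe and no grade above it. Nothing can drop out there, and the protocol already uses grade ≥ 3 for solicited events.
- **That the combined table must show fewer severe events than the solicited table.** The combined table covers 21 days instead of 7, adds unsolicited events and removes serious ones. Its severe count can be lower, equal or higher. A clear mismatch arises only for non-serious fever.
- **That every participant with a fever above 40.0 °C lowers the severe line by one.** A serious event is excluded by design, and a participant with another Grade 3 event stays in any overall line.

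**Conclusion.** The inconsistency is real and minor. As written, SAP 16.1.3 would leave a non-serious Grade 4 fever out of the severe row for fever, and out of an overall severe line when the participant has no other Grade 3 event. Each such case is worth about 1.5 percentage points in a cell of 65.

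This rests on a literal reading of Grade 3, on the planned cell size (the actual denominators may be smaller), and on at least one such fever occurring, for which the documents give no rate. The table is descriptive. No hypothesis, sample size or primary immunogenicity result depends on it, and the solicited safety endpoints are reported through SAP 16.1.1, where the cut is right.

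**What to change.** In SAP 16.1.3, replace Grade 3 with grade ≥ 3 in the breakdown of the combined table. Make the same change in the matching table shell and in the filter that builds it. Leave protocol 9.4.3.2 as it is. The cost is one symbol in the SAP and a check of one shell. No new data, analysis or design change is needed.

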#### **16.1.4. Serious Adverse Events**

SAEs will be summarized and listed as:

- The number and percentage of participants, with exact 95% CIs, with at least one report of SAE with onset after each vaccine administration up to Day 43 and up to study end (i.e., 6 months post-last vaccination) will be summarized.
  - This summary will be repeated for:
    - Causally related SAEs
    - Fatal SAEs
    - Causally related fatal SAEs
    - All SAEs will be included in a listing.

#### **16.1.5. pIMDs**

pIMDs will be summarized and listed as follows:

- The number and percentage of participants, with exact 95% CIs, with at least one report of pIMDs (all pIMDs, causally related) with onset after each vaccination administration up to Day 43 and up to study end (i.e., 6 months post-last vaccination) will be summarized.
- All pIMDs will also be described in detail in a tabular listing. Classification by new onset vs exacerbations of pIMDs will also be presented.

### **16.2. Laboratory Assessments Events**

Laboratory assessments, including CBER grading derivations, to be assessed at Visits 2 and 4 (7 days after each vaccination) are listed in protocol Table 11. These laboratory assessments will be performed for the first 50% of enrolled participants in each age and dose group.

The percentage of participants with an increase in laboratory toxicity grading from baseline after each vaccination

---

Document: \\ieedc-vnasc01\BIOSdata\GSK\H5N8(Flu)\HAB99808\Biostatistics\Documentation\SAP\SAP\SAP v5.0\GSK H5N8-219833\_SAP\_v5.0\_19AUG2024.docx

Author: PPD Version Number: 5.0  
Version Date: 19AUG2024

Template No.: CS\_TP\_BS016 Revision 7

Reference: CS\_WI\_BS005

Effective Date: 01Nov2021

and across vaccinations will be provided with Clopper-Pearson exact 95% CIs. This will be done for each safety laboratory test and across laboratory tests for exposed participants with safety laboratory results available after each vaccination and across vaccination.

Listings will be produced for laboratory assessments.

## **17. DATA NOT SUMMARIZED OR PRESENTED**

The other variables and/or domains not summarized or presented are:

- Physical Examination, pregnancy test

These domains and/or variables will not be summarized or presented, but will be available in the clinical study database, SDTM and/or ADaM datasets.

---

Document:	\ieedc- vnasc01\BIOSdata\GSK\H5N8(Flu)\HAB99808\Biostatistics\Documentation\SAP\SAP\SAP\SAP v5.0\GSK H5N8-219833_SAP_v5.0_19AUG2024.docx		
Author:	PPD	Version Number:	5.0
		Version Date:	19AUG2024
Template No.:	CS_TP_BS016 Revision 7		
Effective Date:	01Nov2021		
			Reference: CS_WI_BS005

